8 ADVERSE EVENTS

See CORE SOP012_v02 for a description of all adverse events, including management and reporting. An 'adverse event' refers to any undesirable clinical occurrence in a participant, whether

it is considered to be device-related or not. Adverse events (AE) may be classified as ‘unanticipated adverse device effects,’ ‘serious adverse events,’ ‘significant adverse events,’ or ‘non-significant adverse events,’ as defined below, Table 4.

A number of conditions may result in temporary suspension until resolution. These include corneal infiltrates, corneal staining, limbal injection, bulbar injection or tarsal conjunctival abnormalities.

Table 4: Classification of types of adverse event

Classification	Definition
Serious Adverse Event	Those events that are life-threatening, or result in permanent impairment of a body function, or permanent damage to a body structure or necessitate medical (therapeutic) or surgical intervention to preclude permanent impairment of a body function or permanent damage to a body structure.
Significant Adverse Event	Those non-serious adverse events that occur with contact lens usage that are not sight-threatening but are usually symptomatic and may warrant therapeutic management and /or temporary or permanent discontinuation of contact lens wear.
Non-Significant Adverse Events	Those less severe non-serious adverse events that occur with contact lens usage that are not sight-threatening, may or may not be symptomatic and may warrant palliative management, such as ocular lubricants or temporary interruption of contact lens wear.
Unanticipated Adverse Device Effect	Adverse events in a study that were not previously identified in the protocol in terms of nature, severity, or degree of incidence. An Unanticipated Serious Adverse Device Effect is an unanticipated adverse event that is serious in nature and caused by or associated with the device and is considered reportable.

AE classification, coding (for reporting to the sponsor) and reporting details, plus examples, are provided in Table 5.

Table 5: Contact lens adverse event classification, coding and reporting guide

Code	Condition	Reporting
Serious Adverse Events		
01	Presumed infectious keratitis or infectious corneal ulcer	For all serious AEs: Notify sponsor as soon as possible, within 24 hours;
02	Permanent loss of ≥ 2 lines of best spectacle corrected visual acuity (BSCVA)	
03	Corneal injury that results in permanent opacification within central cornea (6mm)	
04	Uveitis or Iritis (e.g. presence of anterior segment inflammation as described in ISO 11980, Annex B)	

05	Endophthalmitis	ORE reporting will be within 24 hours as per requirements
06	Hyphema	
07	Hypopyon	
08	Neovascularization within the central 6mm of cornea	
00	Other serious event	
Significant Adverse Events		
11	Peripheral (outside central 6mm), non-progressive, non-infectious ulcer	Notify sponsor as soon as possible, within 5 working days ; ORE reporting as per requirements
12	Symptomatic corneal infiltrative event	
13	Superior epithelial arcuate lesions (SEALs) involving epithelial split	
14	Corneal staining \geq dense coalescent staining up to 2mm in diameter (e.g. moderate, ISO 11980 grade 3)	
15	Corneal neovascularization \geq 1.0mm vessel penetration (e.g. \geq ISO 111980 Grade 2), if 2 grade change from baseline	
16	Any temporary loss of \geq 2 lines BSCVA for \geq 2wks	
17	Any sign and/or symptom for which participant is administered therapeutic treatment or which necessitates discontinuation of lens wear for \geq 2 weeks	
10	Other significant event	
Non-significant Adverse Events		
21	Conjunctivitis (bacterial, viral or allergic)	Notify sponsor as soon as possible, within 5 working days ; ORE reporting as per requirements
22	Papillary conjunctivitis if \geq mild scattered papillae/follicles approximately 1mm in diameter (e.g. ISO 11890 Grade 2), if 2 grade change from baseline	
23	Asymptomatic corneal infiltrative events	
24	Any sign and/or symptom for which temporary lens discontinuation for $>$ 1 day is recommended (if not already classified)	
20	Other sign and/or symptom warranting classification as a non-significant adverse event	

8.1 NORMAL OR ADAPTIVE SYMPTOMS

Transient symptoms such as end-of-day dryness, lens awareness, itching or burning or other discomfort may occur with contact lens wear and may occasionally reduce wearing time. These are

9 DISCONTINUATION FROM THE STUDY

Participants discontinued from a study will be reimbursed \$20 per hour for their active involvement in the study (including the initial screening visit). Participants will be discontinued at the discretion of the investigator or sponsor in consideration of participant safety or protocol compliance, or at discretion of the participant. The following is a list of possible reasons for discontinuation from the study:

- Screening failure: Participants will be discontinued if they do not meet the inclusion and exclusion criteria outlined in section 5.1.3.
- Unacceptable performance with products to be used in study: Participants may be discontinued if they are unable to achieve acceptable comfort and /or vision with the study products.
- Positive slit lamp finding: Participants may be permanently discontinued from the study depending on the severity of the condition and on the judgement of the investigator.
- Adverse event: If a participant experiences an adverse event during the study they may be discontinued based on the clinical judgement of the investigator.
- Symptoms: If the participant has persistent symptoms they may be discontinued based on the clinical judgement of the investigator.
- Disinterest, relocation or illness: The participant may choose to discontinue due to reasons within or beyond their control.
- Violation of protocol or non-compliance: The participant will be discontinued if they are unable or unwilling to follow the protocol specified visit schedules and/or study procedures.
- Instillation of topical ocular medication: The participant will be discontinued if they elect to use a topical ocular medication during the study unless that topical ocular medication is prescribed for a limited duration (less than two weeks) to treat a transient condition; in this case the participant may remain an active participant (at the discretion of the investigator) after stopping topical ocular medication following resolution of the ocular condition).
- Lost to follow-up: The participant will be discontinued if they cannot be contacted and do not return for a final exit visit, and if the investigator has made a reasonable effort to contact the participant for a final study visit.
- Premature termination of the study by the sponsor, CORE or the Office of Research Ethics at the University of Waterloo.

A discontinuation form, stating the reason for discontinuation will be completed, which requires the signatures of both the participant and the investigator, except where the participant is lost to follow-up in which case only the signature of the investigator is required.

When a participant chooses to discontinue from the study they will be given the opportunity to withdraw their data from the statistical analysis. This choice will be captured on the discontinuation form.

All discontinuations including their reasons will be included in the final report.

10 DEVICE MALFUNCTIONS

A device malfunction means the failure of the device to meet its performance specification or otherwise perform as intended. Any defective lens that is *likely* to cause or contribute to a *Serious Adverse Event* should be reported to the Principal Investigator and the sponsor **within 24 hours** of the investigator becoming aware of the malfunction. The ORE would also be notified within 24 hours of any device malfunction that may contribute to a *Serious Adverse Event*.

Other defective lenses should be reported to the Sponsor as soon as possible (usually in weekly study updates to the Sponsor).

This clinical study will also ascertain satisfaction or preference with subjective attributes such as comfort, vision, or lens handling. Responses to these subjective questionnaires will not be considered as complaints or device malfunctions.

11 STUDY COMPLETION AND REMUNERATION

At the last scheduled protocol visit a study completion form will be completed, which requires the signatures of both the participant and the investigator. Once their involvement in the study is complete, participants will be informed about receiving feedback following study completion in the Letter of Appreciation. Participant remuneration will be \$20 per scheduled protocol visit hour (including the initial screening visit). Full details are given in the information consent letter.

12 STATISTICAL ANALYSIS AND DATA MANAGEMENT

12.1 STATISTICAL ANALYSIS

Primary comparisons will be between study lenses, however there are some variables collected over time with the same lens and this time comparison will be analysed (e.g. 'at-home ratings on Days 1, 3 and 5).

All data will be analyzed by CORE at the University of Waterloo. Unmasked data analysis will be conducted using Statistica, SPSS, or other appropriate software. Descriptive statistics will be provided on information regarding baseline variables (age, gender, refractive error distribution, etc.). Table 6 lists the main outcome variables and anticipated statistical procedures. All data will be tested for normality of distribution using Shapiro-Wilk tests.

Results for logMAR will be reported and analysed for binocular acuity and in some cases data of right eye only will be analysed and reported (e.g. lens fit variables, biomicroscopy).

Data from 'at-home' ratings Day 5 will be analysed to determine the mean 'cumulative comfort score', as described by Keir et al.³

A binomial test will be used to analyze the results for the count data of subjective preferences.

Table 6: Statistical analysis to be conducted

Variable	Analysis	Statistical test
Subjective ratings	Descriptive and other statistics	Mean, Median*, Standard Deviation, Minimum, Maximum, Frequency count
	Effect of treatment on outcome variable within subjects (comparison between study days) Effect of time on ratings (comparison over time)	Friedman Wilcoxon matched pairs test
Visual acuity; NITBUT; lens centration and movement; limbal, bulbar and tarsal redness; corneal and conjunctival staining	Descriptive statistics	Mean, Median*, Standard Deviation, Minimum, Maximum, Count
	Effect of treatment on outcome variable within subjects (comparison between study days)	RMANOVA Paired t-test

* For non-parametric data only

The critical alpha level for statistical significance will be set at 0.05, with no adjustments for multiple comparisons.

All participants who were evaluated will be included in the analysis, unless their removal is agreed by the sponsor due to protocol deviations and/or adverse events. In the event of missing data, individual data points will not be extrapolated from the collected data.

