4.1.3 RANDOMIZATION

A randomization schedule will be generated using a web-based program: (for example www.randomization.com) by CORE's Data management team, and provided to the research assistants for the study. The schedule will determine the order of lens wear for participants in the study. Study investigators will remain masked to the randomization schedule until the study is completed and the database has been locked.

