5.3 SCHEDULED AND UNSCHEDULED VISITS

This study has 5 visits. The visits are as follows:

- **Visit 1:** Screening, baseline assessments, fitting of both study lenses.
- **Visit 2:** Dispense lens type #1 (normally combined with Visit 1)
- **Visit 3:** 1-week follow-up assessment of lens type #1 (6 to 10 days after Visit 2), [REDACTED]
- **Visit 4:** Dispense of lens type #2 (normally combined with Visit 3)
- **Visit 5:** 1-week follow-up assessment of lens type #2 and study exit (6 to 10 days after Visit 4), [REDACTED]

A scheduled follow-up visit may only take place when the participant attends wearing the study lenses for 6-8 hours. If this is not the case and the participant is not experiencing any problems with the lenses, the appointment will be rescheduled, ideally within the visit window.

Visits that fall outside of the specified visit windows will be designated as protocol deviations and at the end of the study, the data collected during protocol deviations will be assessed for their suitability to be included in the analysis population.

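### Section 12.1 prescribes an unmasked analysis while some analysis choices remain open; coding the lenses X and Y would be a cheap safeguard against a modest exposure

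*Combined protocol and SAP*

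**What the plan says.** **Analysis (section 12.1).** The study site analyses all data, and "Unmasked data analysis will be conducted using Statistica, SPSS, or other appropriate software". On the tests, "Table 6 lists the main outcome variables and anticipated statistical procedures", although the table's own title is firmer: "Table 6: Statistical analysis to be conducted". As a preliminary step, "All data will be tested for normality of distribution using Shapiro-Wilk tests". A Table 6 footnote reserves the median for non-parametric data, but no sentence links the Shapiro-Wilk result to the choice of test. For eyes, "in some cases data of right eye only will be analysed and reported", with lens fit given as an example.

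**Outcomes (section 2).** The two primary outcomes are single 0-10 ratings, of handling at insertion and at removal, taken at the 1-week visit. The secondary outcomes, centration and post-blink movement, are collected at dispense and at 1 week.

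**Masking (section 4.1.3).** "Study investigators will remain masked to the randomization schedule until the study is completed and the database has been locked". This covers investigators and the schedule. It does not mention the analysts. The site's data management team generates the schedule and gives it to the research assistants.

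**The concern.** A plan that fixes every analysis in advance loses little by being run unmasked. Here the unmasked rule stands beside choices that are not fully closed: the tests are described as anticipated, the normality check has no stated effect on test choice, and each fit outcome has two visits with no rule for which one decides. Whoever settles these points can know which lens is the test product and which the competitor's. Choices made with that knowledge can lean towards one product, and a reader of the report could not rule it out. A two-lens crossover can be analysed in full under neutral labels, so the plan accepts this exposure for little gain.

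**Working it through.** **1. Number analysed.** The plan gives no figure on masking. Its sample size supplies the n. With a difference of 0.8, SD 1.9, two-sided alpha 0.05 and 80% power (section 5.1.1), a paired t-test has standardised effect 0.8/1.9 = 0.421. The noncentral t gives n = 46.23, rounded up to 47, which reproduces the plan. The new completers are 47 - 19 = 28, and n = 28 is used below.

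**2. What to measure.** Knowing lens identity matters only if it lets choices favour a particular lens. The relevant quantity is the chance, with no true difference, of p < 0.05 in favour of one chosen lens. For one fixed two-sided test this is 0.05/2 = 2.5%.

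**3. Choices the documents leave open for movement.** Take the right eye (section 12.1 gives lens fit as an example) and the paired t-test (Table 6), with free choice between the two stated visits.
- If the visits were independent: 1 - (1 - 0.025)² = 1 - 0.9506 = 4.9%.
- If they were perfectly correlated: 2.5%.
- Simulated with an assumed between-visit correlation of 0.4-0.7: about 4-5%.

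A significant result against the chosen lens would then be unavoidable only if both visits showed it. That chance is 2.5% + 2.5% minus 4-5%, or about 0-1%. Fully directed choice of visit would thus turn an even 2.5%/2.5% split into roughly 4-5% against 0-1%.

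**4. A wider menu.** Two eye rules (right eye, or both), three visit rules (dispense, 1 week, or their average) and two tests (t-test, Wilcoxon) make 2 × 3 × 2 = 12 analyses. With assumed correlations of 0.6-0.8 between eyes and 0.4-0.7 between visits, significance favouring one chosen lens is about 6-8%. This menu exceeds the plan: averaging visits appears nowhere, and Table 6 lists Wilcoxon for ratings, not for movement.

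**5. Primary ratings.** There is one rating at one visit, so the open choice considered here is the test: section 5.1.1 assumes a t-test, while Table 6 lists Friedman and Wilcoxon. With rounded normal differences (SD 1.9, n = 28, no true difference), taking the better of t-test and Wilcoxon gives p < 0.05 in either direction in 5.5% of trials, against 5.0% for the t-test alone. In a separate simulation of integer ratings the two tests disagreed at 0.05 in 1.1% of trials with no difference and 3.6% with a true difference.

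**The case against.** **Unmasked analysis after lock is ordinary practice.** This stands. A reader might infer that the plan breaks its own masking, but section 4.1.3 keeps investigators masked until lock and nothing contradicts that. The point rests only on combining a stated unmasked rule with open choices.

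**Table 6 closes more than it seems.** Largely true. A reader might infer that each row offers two rival tests. Friedman may be meant for the at-home ratings on Days 1, 3 and 5 and Wilcoxon for the two-lens comparison. RMANOVA with two levels is equivalent to the paired t-test. The table's title is also firmer than the sentence introducing it.

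**The size is easily exaggerated.** A reader might count any p < 0.05 over all 12 analyses and report about 17% (at correlations 0.6 and 0.4). That counts results in either direction, which an analyst working with X and Y could find just as easily, and several of the 12 analyses are not in the plan.

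**Removals could matter more.** Participants stay in the analysis "unless their removal is agreed by the sponsor due to protocol deviations and/or adverse events", and for out-of-window visits "the data collected during protocol deviations will be assessed for their suitability to be included in the analysis population". A reader might infer that these decisions will be taken with lens identity and results in view. The documents do not say so; they are silent on masking here. Any large figure would have to assume that the least favourable participant happens to have a qualifying deviation or event. Removals are therefore not counted in the size given here.

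**The commercial stake is not stated.** The title page is not available. That the test lens is the sponsor's own product is an inference from section 5.2.3 (its maker may supply the lenses) and section 5.2.5 (worn lenses are shipped to that maker). The inference is strong, but it remains one.

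**Conclusion.** The point holds as a cheap improvement. Section 12.1 prescribes unmasked analysis by the study site, no passage masks the analysts, and a few choices remain open, chiefly which visit decides the fit secondaries. The exposure is about 4-5% significance favouring one chosen lens over the two stated visits, and 6-8% over a menu broader than the plan, against 2.5% for one fixed analysis. These figures assume normal paired differences, n = 28, no true lens difference and the correlations stated above, none of which the documents give; they describe fully directed choice and so are upper limits for each menu. The primary handling ratings are little affected by test choice. Nothing in the documents shows that biased choices were intended.

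**What to change.** In section 12.1, replace the sentence prescribing unmasked analysis with:

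> Analysis will be run on a dataset with lenses coded X and Y; the code is held by a member of the data management team who does not run the analysis, and is broken only after the primary and secondary results tables are final.

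The condition on the code holder is needed because the plan says only that the site analyses the data, so the team that generates the schedule might also run the analysis.

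Do not add a general statement that Shapiro-Wilk never changes the listed test. Centration is a four-category grade, and such a statement could lock a paired t-test onto it.

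**Cost.** One recoded variable, one sentence, and a short wait before products can be named in the tables. No data or visit procedure changes.

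**Limit.** Coding makes any selection even-handed between the lenses; it does not prevent selection. An analyst could still report the smaller of two p-values under code. Only a single pre-named analysis brings the rate back to 2.5% in each direction.

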2 OBJECTIVES

The objective of the study is to evaluate and compare the performance of Alcon's Precision1 lens (P1) to clariti 1 day (C1D), when worn on a daily disposable modality over a period of approximately one week each. C1D is considered the study test lens. P1 will be the control lens.

The primary outcome variables of this study are:

- Subjective ratings for 'Lens handling for lens insertion' (0 - 10 integer scale) for TEST lens compared to CONTROL, collected at the 1-week visit reflecting on a 'typical day' experience during the study;
- Subjective ratings for 'Lens handling for lens removal' (0 - 10 integer scale) for TEST lens compared to CONTROL, collected at the 1-week visit reflecting on a 'typical day' experience.

The secondary outcome variables are:

- Centration (optimal, slight decentration, moderate decentration but not encroaching limbus, excessive & occasionally encroaching limbus), collected at dispense & 1-week visit;
- Post-blink movement in primary gaze, mm, collected at dispense & 1-week visit;

Participants will be randomized to wear either the test or the control lens first. All lenses will be worn in a daily disposable lens wear modality for one week (-1/+3 days). The study involve up to 5 scheduled visits. The study design is shown in Figure 1.

[figure not shown]

Figure 1: Study Design, visits 1 & 2 may be on a single day, also visits 3 & 4 may be on a single day.

Visit 1: Includes screening, baseline assessments, fitting of both study lenses.

Visit 2: Dispense lens pair #1 (either test or control lens, randomized).

Visit 3: 1-week follow-up assessment of lens pair #1

Visit 4: Dispense of lens pair #2 (either test or control lens)

Visit 5: 1-week follow-up assessment of lens pair #2 and study exit.

- Participants will complete the following in-office subjective ratings on paper using a numeric rating scale (0 – 10) at visits 3 and 5 for each lens type:
- Lens handling;
- [REDACTED]
- [REDACTED]
- [REDACTED]
- [REDACTED]

[REDACTED]

[REDACTED]

[REDACTED]

[REDACTED]

- [REDACTED]
- [REDACTED]
- [REDACTED]
- [REDACTED]

- [REDACTED]
- [REDACTED]
- [REDACTED]
- [REDACTED]
- [REDACTED]

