5 STUDY POPULATION

5.1.1 SAMPLE SIZE CALCULATION

[REDACTED]

[REDACTED]

[REDACTED]

[REDACTED]

A total sample size of 47 is recommended to detect a mean difference between lens handling for insertion of 0.8 units on the 0 to 10 scale using a standard deviation of 1.9 with 80% power and alpha 0.05 in a two-tailed t-test. Therefore, the sample size needed for BASSET will be aimed at 28 to complete (i.e. total of 47 minus the 19 completed participants from the BOXER phase 1 pilot study). Therefore, it is recommended that at least 31 subjects are dispensed in the BASSET study, with a target of 28 to complete.

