5.2 STUDY MATERIALS

5.2.1 LENSES

All study lenses are approved by Health Canada. They will be worn bilaterally, and on a daily disposable basis, therefore no lens care solution is required.

Table 1: Details of contact lenses to be used in the study

	Clariti 1-Day – Test (CooperVision, Inc.)	Percision1 – Control (Alcon)
Material	somofilcon A	verofilcon a
HC licence #	81009	101910
Dk/t (barrer/cm)	86	100

Water content	56%	51%
Sphere power (D)	-0.50 to -6.00 (0.25 steps) -6.50 to -10.00 (0.50 steps)	-0.50 to -6.00 (0.25 steps) -6.50 to -10.00 (0.50 steps)
Base curve (mm)	8.6	8.3
Diameter	14.1	14.2
Replacement schedule	Daily disposable	Daily disposable

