7 POTENTIAL RISKS AND BENEFITS TO HUMAN PARTICIPANTS

This is a minimal risk study because of the use of approved products and standard optometric assessments.

Contact lenses in this study will be worn on a daily wear and daily disposable basis. Adverse events and/or complications in the daily wear of soft contact lenses can occur (e.g. inflammation and infection). Complications that may occur during the wearing of contact lenses include discomfort, dryness, aching or itching eyes, excessive tearing, discharge, hyperemia and variable or blurred vision. More serious risks may include photophobia, iritis, corneal edema or eye infection. Although contact lens-related infections are very infrequent, the possibility does exist. The incidence of infection due to daily-wear soft lenses is 0.035%. Almost always an infection will occur only in one eye. Thirty five million Americans who currently wear contact lenses assume this risk.

When contact lenses are worn on a daily wear basis there is a small risk of an adverse event compared to not wearing contact lenses. When contact lenses are worn on an extended wear basis, there is a significantly increased risk of an adverse reaction compared with wearing contact lenses on a daily wear basis.

Additionally, it is possible that participants may experience temporary discomfort associated with the study procedures /products including: burning and stinging, blurred vision, sandiness or grittiness, light sensitivity, dryness, itching, crusty eyes and foreign body sensation.

Participants may not benefit directly from taking part in this study, other than having an opportunity to wear a different contact lens. However, their participation in this study may contribute to scientific research information that may be used in the development of new contact lens products.

Information from this study may help researchers determine new soft contact lens designs to help other people in the future. This study will help the study sponsor to better understand the performance of the products being used in this study.

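### Right-eye-only analysis of lens fit and slit-lamp variables is valid, but gives up some precision on post-blink movement and leaves minor left-eye-only findings out of the analysed tables

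*Combined protocol and SAP*

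**What the plan says.** Section 12.1 reports acuity binocularly and adds that "in some cases data of right eye only will be analysed and reported (e.g. lens fit variables, biomicroscopy"). It does not list which variables fall under this provision, and the visible text gives no reason for choosing one eye and no two-eye summary.

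Section 5.2.1 says of the lenses: "They will be worn bilaterally, and on a daily disposable basis". The trial-fitting step at screening chooses and optimises lens power eye by eye.

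Both secondary outcomes in section 2 are fit variables. Post-blink movement is listed as "Post-blink movement in primary gaze, mm, collected at dispense & 1-week visit". Centration is a four-category grade, also taken at dispense and at one week. Section 5.3.3 lists both under the fit assessment. Table 6 assigns fit, redness and staining variables to "RMANOVA Paired t-test".

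The primary outcomes are participant-level handling ratings, for example "Subjective ratings for 'Lens handling for lens insertion' (0 - 10 integer scale) for TEST lens compared to CONTROL".

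**The concern.** If both eyes wear the same lens in each period and both are graded, a right-eye analysis sets aside half the eye-level data on the only two named secondary outcomes. The usual reason for using one eye is to avoid treating two correlated eyes as independent. That reason does not require dropping an eye, because the mean of the two eyes is also one value per participant and fits the same paired test.

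For slit-lamp signs the issue is completeness. A participant with mild staining or redness in the left eye only would count as unaffected in a right-eye table, although Table 6 lists those signs for comparison between lenses.

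At stake are somewhat wider intervals for post-blink movement and other continuous fit measures, and a mild under-count of low-grade one-sided signs.

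**Working it through.** **The plan's own figure.** Section 5.1.1 states: "A total sample size of 47 is recommended to detect a mean difference between lens handling for insertion of 0.8 units", with SD 1.9, 80% power and two-sided alpha 0.05. A paired t-test with d = 0.8/1.9 = 0.421 gives power 79.8% at n = 46 and 80.7% at n = 47, so 47 reproduces. It concerns insertion handling only. No power is stated for centration or movement.

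**Precision for a continuous fit measure.** Let D_R and D_L be a participant's test-minus-control differences in the right and left eye, with equal variance s² and correlation r. Then

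Var[(D_R + D_L)/2] = s²(1 + r)/2, so SE(two-eye mean)/SE(one eye) = sqrt((1 + r)/2).

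Here r is the correlation of the lens differences, not of the raw values. Stable person effects cancel in a crossover, so a high correlation in raw grades does not ensure a high r. The documents give no value, so a range is assumed. The table uses the 28 target completers of section 5.1.1. The minimum detectable difference (MDD) is for 80% power at two-sided 0.05, in units of s. On one eye it is 0.549. The power column is for a true difference of 0.549 s, which has 80% power on one eye.

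| Assumed r | SE ratio, two-eye to one-eye | One-eye SE larger by | MDD, two-eye mean | Power, two-eye mean | Equivalent one-eye n, 28 × 2/(1+r) |
|---|---|---|---|---|---|
| 0.5 | 0.866 | 15.5% | 0.476 | 89.9% | 37.3 |
| 0.7 | 0.922 | 8.5% | 0.506 | 86.0% | 32.9 |
| 0.8 | 0.949 | 5.4% | 0.521 | 84.0% | 31.1 |
| 0.9 | 0.975 | 2.6% | 0.535 | 82.0% | 29.5 |

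At r = 1 nothing is lost. The formula applies to a mean of two eyes; it does not apply to a worse-eye score.

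**Left-eye-only slit-lamp findings.** Assume a per-eye rate p and a between-eye correlation c, neither of which is in the documents. Then both eyes = p² + c·p(1−p), left eye only = p − both, and either eye = 2p − both.

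| p | c | Both | Left only | Either | Left only / either | Left only × 28 |
|---|---|---|---|---|---|---|
| 0.05 | 0.3 | 0.0168 | 0.0333 | 0.0833 | 40% | 0.93 |
| 0.05 | 0.8 | 0.0405 | 0.0095 | 0.0595 | 16% | 0.27 |
| 0.10 | 0.3 | 0.0370 | 0.0630 | 0.1630 | 39% | 1.76 |
| 0.10 | 0.8 | 0.0820 | 0.0180 | 0.1180 | 15% | 0.50 |

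So roughly 15% to 40% of participants with a finding in either eye would be missing from a right-eye table. In absolute terms that is about 0.3 to 1.8 of 28 participants per lens.

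**What adverse event reporting already catches.** Section 8 defines adverse events per participant, whichever eye is involved. Table 5 codes presumed infectious keratitis (01), symptomatic and asymptomatic infiltrates (12, 23), staining from ISO grade 3 (14) and conjunctivitis (21). Neovascularization (15) and papillary conjunctivitis (22) need a two-grade change. Limbal and bulbar redness have no code of their own, only the catch-all entries. What a right-eye table can lose is therefore lower-grade staining and redness.

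**The case against.** The strongest reply is that nothing here is wrong. A pre-named eye gives one unbiased value per participant, the two lenses are compared in the same eye of the same person, and the paired tests are valid. Any omission applies equally to both lenses. The gain from averaging rests on an unknown correlation and is under 3% at r = 0.9. All of this stands, and it is why the point is one of efficiency and completeness only.

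A reader might go further in three ways that the documents do not support.

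- **That left-eye infections would be lost.** Section 7 says "Almost always an infection will occur only in one eye", which invites this reading. But infection is a serious adverse event under Table 5, reported to the sponsor within 24 hours for either eye, and section 9 puts all discontinuations in the final report.
- **That the left eye is always discarded.** The provision covers some cases, with examples. Parts of the fit and slit-lamp procedures are redacted, so per-eye grading of every measure is implied but not confirmed.
- **That a worse-eye analysis is the natural remedy.** It can set the left eye under one lens against the right eye under the other. That loses same-eye pairing and changes what is estimated.

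**Conclusion.** The concern holds in a limited form. Section 12.1 allows a valid but less precise analysis of post-blink movement and other continuous fit measures. The two-eye mean would have a standard error 0.87 to 0.97 of the one-eye value for an assumed r of 0.5 to 0.9, given equal variance in the two eyes and grading of both. Separately, left-eye-only signs below the adverse-event threshold leave the analysed tables. On assumed rates this is at most about two of 28 participants per lens.

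It would be wrong to infer bias, an inflated error rate, or any effect on the handling outcomes, the sample size of 47 or adverse event reporting. Label: cheap improvement.

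**What to change.** Provided both eyes are graded, amend section 12.1 as follows.

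1. For post-blink movement and other continuous fit measures (such as push-up tightness), enter the participant's mean of both eyes per lens and visit into the Table 6 paired tests. Do not enter the two eyes as independent observations.
2. For staining and redness, add a descriptive count per lens of participants with a finding in either eye.
3. Keep the right-eye results as a supplementary listing, and name the variables to which each rule applies.
4. Leave the comparisons of centration and biomicroscopy on a same-eye basis; do not replace them with a worse-eye comparison.

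The cost is a change of wording and a little more analysis, with no extra visit, procedure or participant. The one downside is that the main fit result becomes less directly comparable with earlier right-eye reports, which the supplementary listing largely offsets.
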